7.2.3 Post-Injection

The following procedures will be completed at the specified timepoints:

- 0-30 Minutes Post-Injection
 - ECG (completed before vital signs)
 - Vital signs (body temperature, heart rate, systolic and diastolic blood pressure, and respiratory rate) will be collected
 - Assessment of adverse events
- 60-75 Minutes Post-Injection
 - Assessment of adverse events
 - Whole body planar imaging
 - Optional SPECT/CT region(s) of interest imaging
- After the 60-75 Minute Imaging:
 - Clinical labs and urinalysis will be performed.
 - A KS tissue biopsy will be taken of an imaging-visualized non-visceral lesion

- If no lesion is visualized on imaging, a lesion of at least 5-6 mm in a clinically accessible area will be biopsied as chosen by the Investigator(s) who will record selection and rationale
- A photograph of the biopsy site with a measurement scale must be taken and stored with the subject's research chart

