8.4 Post-Injection and Imaging Biopsy Acquisition

The purpose of the KS lesion biopsy will be to determine the proportion of CD206-expressing cells and quantity of CD206 (IHC fluorescence) in KS tissues in parallel with an analysis of KS imaged with Tc 99m tilmanocept. A non-visceral site of KS for biopsy post-imaging in each subject will be chosen by the Nuclear Medicine physician based on visualized localization and lesion size. If no lesion is determined to localize Tc 99m tilmanocept, a lesion of at least 5-6 mm in a clinically accessible area will be biopsied as chosen by the Investigator(s) who will record selection and rationale.

All subjects will receive the biopsy on the day of IV Tc 99m tilmanocept administration at the completion of imaging.

A biopsy up to 6mm of the designated lesion will be taken, and a photograph of the biopsy site with a measurement scale will be taken and stored with the subject's research chart. The tissue will be obtained at the completion of Tc 99m tilmanocept IV injection and imaging and delivered on ice to the Department of Pathology at Zuckerberg San Francisco General Hospital. The biopsy will be sectioned into a formalin-fixed paraffin-embedded (FFPE) segment and a fresh or frozen segment to be used for other analyses. FFPE tissue sections will be quantified for CD206 and LANA through a standardized quantitative image analysis program. HHV8 will be quantified by qPCR.

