9.3 Efficacy Variables

The efficacy variables for this study are as follows:

- Nuclear medicine specialist determination of presence/absence of illumination (i.e., localization positive/negative, anatomic site) relative to background from SPECT imaging results for each subject;
- Clinically identified presence/absence of KS (based on any previous diagnostic evaluations);
- Quantitative SPECT gamma counts for each biopsied lesion.

The efficacy endpoints for this study are as follows:

- Per subject localization rate of Tc 99m tilmanocept in at least one KS suspected or confirmed lesion by planar and/or SPECT/CT imaging
- Per lesion/region concordance of Tc 99m localization with anatomical areas of active KS defined by confirmed diagnosis or clinical symptomology
- Localization intensity for each biopsied and clinically defined lesion as determined by quantitative SPECT gamma counts
- Per biopsied lesion proportion of CD206-expressing cells and total CD206 as determined by histology and relative IHC fluorescence
- Per lesion/region concordance of IV vs SC Tc 99m localization with anatomical areas of active KS defined by confirmed diagnosis or clinical symptomology.
- Per subject localization rate of Tc 99m tilmanocept in areas other than KS by planar and/or SPECT/CT imaging

- Per area localization rate of Tc 99m tilmanocept in the most frequently identified areas other than KS by planar and/or SPECT/CT imaging

A localized subject is one for whom Tc 99m by planar and/or SPECT/CT imaging results in the illumination of at least one site relative to background as determined by the nuclear medicine specialist.

A localized KS lesion is a lesion that is both clinically identified or suspected KS and planar or SPECT/CT illuminated.

Localization in areas other than KS will also be defined per subject and per area, where these areas are clinically negative KS locations based on clinical symptomology.

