9.5.3 Analysis of Efficacy Variables

The number and percentage of subjects with at least one biopsy-confirmed or clinically suspected KS lesion that has localized with Tc 99m tilmanocept by planar and/or SPECT/CT imaging will be

computed. A 95% exact confidence interval on the per subject localization rate will be computed. This analysis will be performed by dose.

Per region lesion localization of Tc 99m tilmanocept by planar and/or SPECT/CT imaging will be computed across all biopsy-confirmed or clinically suspected KS lesions of all subjects. A 95% exact confidence interval on per region lesion localization will be calculated. This analysis will be performed by dose.

Localization intensities of biopsied lesions will be summarized by descriptive statistics (mean, median, standard deviation, minimum, maximum and range) for each dose.

Per biopsied lesion proportion of CD206-expressing cells and quantity of CD206 as determined by histology and IHC fluorescence will be summarized by descriptive statistics (mean, median, standard deviation, minimum, maximum and range) for each dose.

Concordance between between IV and SC tilmanocept in biopsy-confirmed or clinically suspected KS lesion sites will be assessed with a cross-tabulation including the joint probability distribution. The site will be the sampling unit for this analysis. An exact version of McNemar's test will be performed, testing the null hypothesis

$$H_0: \pi_{IV} = \pi_{SC}$$

$$H_A: \pi_{IV} \neq \pi_{SC}$$

where π_{IV} and π_{SC} represent the probabilities of localization with IV (only) tilmanocept and localization with SC tilmanocept only respectively.

In addition, descriptive statistics will be generated relative to the concordance and reverse concordance of observed sites of discrete localization of Tc 99m tilmanocept following IV and SC administration.

The number and percentage of subjects with at least one anatomical site other than KS that has been localized with Tc 99m tilmanocept by SPECT imaging will be computed. A 95% exact confidence interval on the per subject localization rate will be computed. This analysis will be performed by dose and overall.

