4.0 Analysis of Efficacy

4.1 Description of Efficacy Variables

Secondary objectives of the study are to determine the concordance between clinical assessment/diagnosis and the localization of Tc 99m tilmanocept by planar and/or SPECT/CT imaging in cutaneous and non-cutaneous sites of KS; to qualify and quantify Tc 99m tilmanocept localization intensity on imaging with CD 206 locale and quantity by histology and IHC in biopsied KS lesions to determine the optimal IV dose; and concordance of localization of Tc 99m tilmanocept via IV and SC routes of administration by planar and/or SPECT/CT imaging in cutaneous and non-cutaneous sites of KS. The relevant endpoints are the following:

- Per subject localization rate of Tc 99m tilmanocept in at least one KS suspected or confirmed lesion by planar and/or SPECT/CT imaging
- Per lesion/region concordance of Tc 99m localization with anatomical areas of active KS defined by confirmed diagnosis or clinical symptomology

- Localization intensity for each biopsied and clinically defined lesion localized on imaging following IV injection as determined by quantitative SPECT gamma counts
- Per biopsied lesion proportion of CD206-expressing cells and proportion of HHV8-expressing cells as determined by histology and relative IHC fluorescence
- Per lesion/region concordance of IV vs SC Tc 99m localization with anatomical areas of active KS defined by confirmed diagnosis or clinical symptomology.
- Per subject localization rate of Tc 99m tilmanocept in areas other than KS by planar and/or SPECT/CT imaging
- Per area localization rate of Tc 99m tilmanocept in the most frequently identified areas other than KS by planar and/or SPECT/CT imaging

An exploratory objective of the study is to use quantitative Polymerase Chain Reaction (qPCR) methods to measure the amount of Human Herpes Virus 8 (HHV8) present in the biopsy tissue.

The relevant variables are the following:

- Nuclear medicine specialist determination of presence/absence of illumination (i.e., localization positive or negative per anatomic site) relative to background from planar and/or SPECT/CT imaging results for each subject;
- Clinically identified presence or absence of KS based on any previous diagnostic evaluation;
- Proportion of CD206-expressing cells (IHC fluorescence);
- Quantitative SPECT gamma counts for each biopsied lesion localized on imaging following IV injection; and,
- HHV8 concentrations as determined by qPCR for each biopsied lesion.

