4.2 Analysis of Efficacy Variables

Localization in KS Sites

The number and percentage of subjects with at least one biopsy-confirmed or clinically suspected KS lesion that has localized with Tc 99m tilmanocept by planar and/or SPECT/CT imaging will be computed. A 95% exact confidence interval on the per-subject localization rate will be computed. This analysis will be performed by dose group and route of administration.

Per-lesion/region localization of Tc 99m tilmanocept by planar and/or SPECT/CT imaging will be computed across all biopsy-confirmed or clinically suspected KS lesions of all subjects. A 95% exact confidence interval on the per-lesion/region localization will be calculated. This analysis will be performed by dose group and route of administration.

An analysis table will also be provided to display the counts of KS lesions localized by imaging that were not previously identified clinically.

Concordance between IV and SC tilmanocept in biopsy-confirmed or clinically-suspected KS lesion sites will be assessed with a cross-tabulation of the IV and SC findings, including the joint probability distribution. The sampling unit for this analysis will be the site. An exact conditional version of McNemar's test will be performed to test the hypotheses

$$H_0: \pi_{IV} = \pi_{SC}$$
$$H_A: \pi_{IV} \neq \pi_{SC},$$

where π_{IV} and π_{SC} represent the probabilities of localization with IV (only) tilmanocept and SC (only) tilmanocept, respectively. In addition, the number and proportion of subjects with concordance and reverse concordance of observed sites of discrete localization of Tc 99m tilmanocept following IV and SC localization will be summarized.

Localization Intensity by Planar and/or SPECT/CT Imaging

Tc 99m tilmanocept average pixel intensity and percent above background will be summarized with descriptive statistics (mean, standard deviation, minimum, median, maximum, and range) for each biopsied lesion localized on imaging following IV injection of Tc 99m tilmanocept by dose group. Summary statistics will be presented separately by imaging type (planar, SPECT/CT).

Proportion of CD206-expressing Cells

Per biopsied-lesion proportion of CD206-expressing cells as determined by histology and IHC fluorescence will be summarized by descriptive statistics (mean, standard deviation, minimum, median, maximum, and range) by dose group.

Localization in Non-KS Sites

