7.0 List of Analysis Tables, Figures and Listings

Table No.	Table Title	Included in Final Tables	Shown in Appendix B
1	Subject Disposition by Cohort	X	X
2	Demographics and Baseline Data Summary Statistics by Cohort – Continuous Variables (Safety Population)	X	X
3	Demographics and Baseline Data Summary Statistics by Cohort – Categorical Variables (Safety Population)	X	X
4	Summary of Study Drug Administration by Cohort (Safety Population)	X	X
5	Subject-Level Localization of KS Lesions – Nuclear Medicine Findings (ITD Population)	X	X
6	Lesion-Level Localization of KS Lesions – Nuclear Medicine Findings (ITD Population)	X	X
7	Additional KS Lesions Identified from Imaging That Were Not Seen Clinically – Nuclear Medicine Findings (ITD Population)	X	X
8	Lesion-Level Non-Localization of KS Lesions – Nuclear Medicine Findings (ITD Population)	X	X
9	Number and Percentage of Concordant and Reverse Concordant Lesions (ITD Population)	X	X
10	Summary of Imaging-Localized Biopsied Lesion Localization Intensity by Cohort – Imaging = Planar (ITD Population)	X	X
11	Summary of Imaging-Localized Biopsied Lesion Localization Intensity by Cohort – Imaging = SPECT/CT (ITD Population)	X	X
12	Summary of Per Biopsied Lesion Proportion of CD206-Expressing Cells and Proportion of HHV8-Expressing Cells by IHC (ITD Population)	X	X
13	Summary of Per Biopsied Lesion HHV8 Quantitation by qPCR (ITD Population)	X	X
14	Subject-Level Localization in Areas Other Than KS Sites – Nuclear Medicine Findings (ITD Population)	X	X
15	Site-Level Localization in Areas Other Than KS Sites – Nuclear Medicine Findings (ITD Population)	X	X
16	Number and Percent of Subjects with Adverse Events (Safety Population)	X	X
17	Summary of Adverse Events (Safety Population)	X	X
18	Number and Percent of Subjects with Treatment Emergent Adverse Events (Safety Population)	X	X
19	Summary of Treatment Emergent Adverse Events (Safety Population)	X	X
20	Number and Percent of Subjects with Adverse Drug Reactions (Safety Population)	X	X
21	Number and Percent of Subjects with Serious Adverse Events (Safety Population)	X	X
22	Vital Sign Parameters Summary Statistics (Safety Population)	X	X

Table No.	Table Title	Included in Final Tables	Shown in Appendix B
23	Vital Sign Shift Table (Safety Population)	X	X
24	Clinical Laboratory Parameters Summary Statistics (Safety Population)	X	X
25	Clinical Laboratory Parameters Shift Table (Safety Population)	X	X
26	Electrocardiogram Parameters Summary Statistics (Safety Population)	X	X

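### The SAP limits the intensity summary to biopsied lesions that localized, so the mean by dose depends on localization and covers different lesions from the CD206 summary

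*SAP*

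**What the plan says.** Protocol 9.3 lists the endpoint as "Localization intensity for each biopsied and clinically defined lesion as determined by quantitative SPECT gamma counts". Protocol 9.5.3 plans the analysis by dose: "Localization intensities of biopsied lesions will be summarized by descriptive statistics". Neither sentence requires the lesion to have been seen on the scan.

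The biopsy rule is in Protocol 7.2.3 and is repeated for Cohort 3 in 7.5.3. The first choice is a visible lesion: "A KS tissue biopsy will be taken of an imaging-visualized non-visceral lesion". The fallback is: "If no lesion is visualized on imaging, a lesion of at least 5-6 mm in a clinically accessible area will be biopsied". Protocol 8.4 repeats the fallback and has every subject biopsied after the IV imaging.

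The SAP adds a condition in three places:

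- SAP 4.1, endpoint list: "Localization intensity for each biopsied and clinically defined lesion localized on imaging following IV injection as determined by quantitative SPECT gamma counts". The variable list in the same section has the same limit.
- SAP 4.2, analysis: "for each biopsied lesion localized on imaging following IV injection of Tc 99m tilmanocept by dose group".
- SAP 7.0, titles of Tables 10 and 11: "Summary of Imaging-Localized Biopsied Lesion Localization Intensity by Cohort".

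No reason is given, and no companion summary of the other biopsied lesions is planned. The CD206 paragraph of SAP 4.2, and Table 12, cover each biopsied lesion with no localization condition. Protocol 2.2 and SAP 1.0 give the purpose: to read intensity together with CD206 in biopsied lesions so as to find the optimal IV dose.

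**The concern.** Whether a lesion localizes is itself an uptake result. Selecting on it before averaging uptake removes the low readings from the average, and it removes more of them at the dose that localizes less often. The biopsy rule already prefers a visible lesion; the SAP condition then drops the subjects for whom no visible lesion was available.

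Two things are at stake, both in a secondary objective. First, the mean intensities by dose in Tables 10 and 11 can look alike, or even change order, when uptake across the biopsied lesions differs. Second, the lesions with the least uptake, which say most about whether uptake follows CD206, have a CD206 value in Table 12 but no intensity in Tables 10 and 11. The two summaries then describe different sets of lesions.

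**Working it through.** **Plan's own figure.** Cohorts of 4, 4 and up to 6 (SAP 1.1 and 1.3) give 4 + 4 + 6 = 14 subjects, as stated. With one designated lesion per subject, at most 14 post-IV biopsies are planned. The documents give no intensity value, spread or target, so there is no intensity figure to reproduce.

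**Lesion sets side by side.**

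| Subject's IV scan | Lesion biopsied | In Tables 10-11 (SAP) | In Table 12 (CD206) | In Protocol 9.5.3 summary |
|---|---|---|---|---|
| Suitable lesion visible | Visible lesion | Yes | Yes | Yes |
| Nothing visible | Fallback lesion | No | Yes | Yes |

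**Effect on the mean.** Let n subjects be biopsied at a dose and k have a localized biopsied lesion. Assume localized lesions read L% above background and fallback lesions b%.

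- SAP rule: mean = L, whatever k is (k at least 1).
- All biopsied lesions: mean = (kL + (n − k)b)/n.

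Compare dose A (k = 4, n = 4) with dose B (k = 1, n = 4). All values of L and b are assumptions.

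| L | SAP rule, A and B | All biopsied, A | B, b = 0 | B, b = 10 | B, b = 20 |
|---|---|---|---|---|---|
| 50 | 50 and 50 | 50 | 12.5 | 20 | 27.5 |
| 100 | 100 and 100 | 100 | 25 | 32.5 | 40 |
| 200 | 200 and 200 | 200 | 50 | 57.5 | 65 |

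For example, (1 × 100 + 3 × 20)/4 = 160/4 = 40.

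The order can reverse. If B's one localized lesion reads 120 and A's four read 100, the SAP rule puts B ahead, 120 to 100. All biopsied lesions give B 120/4 = 30 with b = 0, or (120 + 60)/4 = 45 with b = 20, against A's 100.

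**How often a lesion is dropped.** Let p be the assumed chance that a subject has a visible lesion suitable for biopsy, with subjects independent. P(at least one dropped) = 1 − pⁿ, and the expected number left in the table is np.

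| p | n = 4: P(dropped), expected left | n = 6: P(dropped), expected left |
|---|---|---|
| 0.50 | 1 − 0.0625 = 0.94, 2.0 | 0.98, 3.0 |
| 0.75 | 0.68, 3.0 | 0.82, 4.5 |
| 0.90 | 0.34, 3.6 | 0.47, 5.4 |
| 1.00 | 0, 4 | 0, 6 |

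If every subject has a visible lesion, the two rules agree.

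**What the rate table adds.** The exact two-sided 95% interval is 0.006 to 0.806 for 1/4 and 0.398 to 1.000 for 4/4. Table 5 would show the contrast in counts, but with overlapping intervals.

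**The case against.** A reader might infer that, under this SAP, a dose that rarely localizes would pass as equal to one that always does. The documents do not support that. Table 5 reports localization per subject, Table 6 per lesion, and Table 8 the lesions not localized, all by cohort and route. Tables 10 and 11 print n. In the example above, Table 5 would show 4/4 against 1/4 and Table 10 would show n = 4 against n = 1.

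A reader might also infer that a planned test between doses, or a planned correlation with CD206, is biased. Neither is planned: SAP 2.1 makes the results descriptive, and SAP 4.2 has no such analysis of intensity. What is affected is a descriptive summary serving a stated objective.

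Three further points have weight.

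- The footnote to Listing 17 covers clinically identified, biopsied lesions without a localization condition, and Listing 19 gives CD206 by subject. With one designated biopsy each, the two could be matched by subject number. This softens the problem, but the SAP text nowhere says that fallback lesions will be measured.
- The phrase localization intensity can be taken to presuppose localization, and a rate followed by intensity among localized lesions is a legitimate two-part display. That is a reason to keep the localized-only summary, not to make it the only one.
- Restoring fallback lesions does not undo the choice of a visible lesion when there is one. This stands; Table 6 is the output that speaks to it.

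**Conclusion.** The concern holds in a limited form. SAP 4.1, 4.2 and Tables 10 and 11 narrow the protocol's lesion set without explanation. The intensity means by dose become conditional on localization and stop matching the lesions in Table 12. The fault lies in those means and their pairing with CD206; the localization outputs are sound on this point, and the primary safety endpoint is untouched.

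The size depends on how many subjects have no visible lesion, which the documents do not predict. In the central illustration, equal SAP means of 100 correspond to 100 against 25 to 40 over all biopsied lesions. This rests on assumed intensities and on an assumed split of 4/4 against 1/4. The protocol-SAP difference itself rests on the text alone. It should be corrected, because intensity is one of the inputs named for the dose choice and cohorts of 4 to 6 leave little to average once lesions are dropped.

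**What to change.** In SAP 4.1, 4.2 and Table 10, make all biopsied lesions the main intensity summary, as in Protocol 9.5.3. Measure each by a region of interest at the known biopsy site on the planar image, which every subject has. Keep the localized-only summary as a supplementary row, and print number localized / number biopsied beside each mean. In Table 11, include every biopsied lesion that the optional SPECT/CT covered. List each lesion's intensity next to its CD206 value in one listing. While the shells are open, reconcile their rows with the text: Tables 10 to 12 have no Cohort 1 row, although SAP 4.2 promises summaries by dose group.

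The cost is SAP wording and a few extra readings on images already held; no visit, scan or biopsy is added. Readings at non-visualized lesions will be less precise. The protocol requires a biopsy-site photograph with a scale but describes no marker or image registration, so the SAP should state how the region is placed. Table 11 may still lack some fallback lesions, and the preference for biopsying a visible lesion remains; the SAP should point to Table 6 for that.

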5.0 Analysis of Safety

Adverse Drug Reactions (ADRs) are defined as all noxious and unintended responses to a medicinal product related to any dose or dose regimen. The phrase 'responses to a medicinal product' means that a causal relationship between a medicinal product and an adverse event. The primary safety variable is the proportion of patients experiencing at least one ADR. The number and percentage of subjects with ADRs will be tabulated by dose group and overall. Other safety endpoints are noted below.

Analysis of Safety Endpoints

Attention shall be paid to the occurrence of adverse events (AEs) from the time of signing informed consent until exit from the study. Events occurring prior to Tc 99m tilmanocept administration will be recorded in the subject's medical history unless determined to be related to the study procedure. A treatment emergent adverse event (TEAE) is defined as an adverse event whose start date is on or after the first study drug administration date. If the study drug administration date and/or the AE start date are missing, the AE will be considered treatment emergent.

Prior to analysis, all AEs will be coded using the Medical Dictionary for Regulatory Activities (MedDRA). The MedDRA version used will be stated in the final validated tables. Based on these coded terms, AEs and TEAEs will be summarized by dose group and overall as follows:

- by system organ class and preferred terms;
- by system organ class and preferred terms and relation to study drug; and,
- by system organ class and preferred terms and severity.

In addition to the above endpoints, the following describes the analyses of the other safety data being collected for the study.

Vital Signs

Vital signs will include heart rate, blood pressure, respiration rate, and body temperature. Vital signs will be taken during screening, prior to study drug administration on Day 1 (and Day 7 [\pm 3] for Cohort 3), and within 30 minutes following study drug administration. For each vital sign, summary statistics

(mean, standard deviation, minimum, median, maximum, range, n) on the raw values as well as their changes from pre-injection on Day 1 (and Day 7 [\pm 3] for Cohort 3) will be presented by dose group and overall. Time points included in this analysis are Day 1 (and Day 7 [\pm 3] for Cohort 3) within 30 minutes pre-injection and within 30 minutes post-Injection. If repeat vital signs are taken at a given time point, then the last measurement will be used for the analysis tables. A shift table will be created showing shifts Abnormal/Abnormal, Abnormal/Normal, Normal/Abnormal, Normal/Normal from pre-injection to post-injection of Tc 99m tilmanocept. This analysis will be performed by dose group and overall.

All vital signs will be listed, including those not presented in the analysis tables.

Physical Exams

A complete physical exam will be performed during screening. A data listing of the physical exam results will be created as shown in [Appendix B](#).

Concomitant Medications

All concomitant medications will be coded with WHO Drug Dictionary (Uppsala Monitoring Centre) version March 2017 or later. A data listing will be constructed with Preferred Term, Verbatim Term, ATC Level 1 Code, and ATC Level 4 Code. A summary table will be provided to show the counts and percentages of subjects taken medications by ATC Level 4 Code and Preferred Term by dose group and overall.

Clinical Laboratory Parameters

Changes in hematology, clinical serum chemistry and urinalysis between screening (i.e., baseline) and the post-injection time point will be calculated, and descriptive statistics will be calculated on the raw and change from baseline values by dose group and overall. A copy of the normal laboratory values for all laboratories utilized for this study will be submitted to the Sponsor (or designee) prior to initiation of the study. A shift table will be created showing shifts Abnormal/Abnormal, Abnormal/Normal, Normal/Abnormal, Normal/Normal from screening baseline to post-injection of Tc 99m tilmanocept. This analysis will be performed by dose group and overall.

ECG

ECG recordings will be obtained during screening (i.e., baseline) and within 30 minutes following study drug administration. ECG parameters (heart rate, PR interval, QRS interval, QT interval, and QTcF interval) will be summarized as raw values and change-from-baseline (CFB). A shift table will be created showing shifts Abnormal/Abnormal, Abnormal/Normal, Normal/Abnormal, Normal/Normal from screening baseline to post-injection of Tc 99m tilmanocept. Both the quantitative and shift table analyses will be performed by dose group and overall.

